## **6.0 STUDY PARAMETERS**

Parameters	Baseline (Pre-Op)	72 Hrs Post- Op	2-3 Weeks Post-Op
MRI	X	X	X

## **7.0 CORRELATIVE STUDIES (if applicable)**

This is not a correlative study.

## **8.0 STATISTICAL CONSIDERATIONS**

Power analysis was not performed for this pilot study, since magnitude of differences is unknown. Obtained data will be used for designing a larger study. Kappa statistics will be calculated to evaluate the inter-rater reliability for the primary aim. For the secondary aims, descriptive statistics will be used.

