### *Primary aim:*

Assess if Magnetic Resonance Imaging (MRI) at 2 to 3 weeks after surgery (aka: later imaging) leads to the same clinical decisions and has the same probability of being chosen by a physician for guiding the subsequent management of the patient, compared with immediately postoperative MRI (within 72 hours, aka: early imaging).

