### *Secondary aims:*

Investigate the differences between early and late MRI by comparing:

Size of tumor in three dimensions;

Extent of edema;

Presence and extent of fluid collection;

Spine Oncology Study Group score;

Involvement of adjacent levels;

Progression of tumor;

Patient's preference/performance scale right after each image had taken: level of discomfort (measured by visual analog scale) at around the time (within 48 hours) each MRI was performed.

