### *Sample:*

Patients admitted to Cleveland Clinic for surgical management of metastatic extradural spinal tumors will be considered for the study. We anticipate the initial enrollment of 8 patients, which is a number chosen arbitrary for the pilot study. Based on results of this study we will perform power analysis and determine the number of subjects needed to get statistically significant results. Inclusion will not depend in any way on age, gender, ethnicity, or any other personal characteristics other than clinical relevance. We expect the study population to be similar to the spine surgery population seen at the Cleveland Clinic for neoplastic pathologies.

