### **5.0 RESEARCH PLAN**

#### *Imaging protocol:*

We will identify the patients meeting the above criteria and consent them for the study. Another MRI will be obtained 2-3 weeks postoperatively. The routine spine MRI protocol will be utilized, which includes the following sequences: haste localizer, sagittal T1, T2, and STIR, axial T2 for lumbar spine or axial gradient echo for cervical and thoracic spine, axial T1, post contrast sagittal and axial T1. All scans will be obtained using a 1.5 Tesla magnet. When indicated, sedation or anxiolysis and IV hydration for low glomerular filtration rate will be administered by radiology per protocol.

*Image analysis:*

The image acquisition dates will be blinded and the images independently reviewed by two neuroradiologists, a radiation oncologist, and a spine surgeon. Each of them will compare and choose a better-quality image. These results will be compared and inter-observer variability will be established.

Radiology (2 independent neuro-radiologists) will be blinded to all quantitative data (including the date of post-op MRI) and they will be asked to evaluate the following parameters:

- a. Level(s) of surgery = number ie L3, L4
- b. Presence of hardware = Y or N
- c. Does hardware obscure canal = Y or N
- d. Nature of surgery = 0 separation surgery/decompression only, 1 corpectomy, 2 combination of 0+1
- e. Fluid collection = AP\*Lateral\*CC in CM
- f. Epidural disease pre op = SOSG grading system AND max thickness at N level
- g. Epidural disease post op = SOSG grading system AND max thickness at N level
- h. Nature of marrow replacement (preop and residual on post op) = 1-4 for 25%, 50%, 75%, and 100% replaced respectively
- i. Compression fracture pre and post = Y or N
- j. Adjacent level involvement pre and post = Y or N

Spine surgeon and radiation oncologist will be blinded to date and use a scale of

- a. 0 = not confident,
- b. 1 = confident
- c. 2 = very confident

in terms of confidence in contouring/tumor targeting using a particular image set

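### The only analysis named for the primary aim is inter-rater kappa, which compares readers and gives no late-versus-early result

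*Combined protocol and SAP*

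**What the plan says.** - **The question.** Section 2.0, Primary aim, asks whether late MRI "leads to the same clinical decisions and has the same probability of being chosen by a physician", compared with early MRI. This is a within-patient contrast between two scans.
- **The analysis for that question.** Section 8.0: "Kappa statistics will be calculated to evaluate the inter-rater reliability for the primary aim". The type of kappa is not named.
- **Early-late comparisons elsewhere.** The secondary aims "Investigate the differences between early and late MRI by comparing" a list of imaging features and patient discomfort, and Section 8.0 adds: "For the secondary aims, descriptive statistics will be used". Neither the physician's choice nor a clinical decision is on that list.
- **Data collected.** Section 5.0, Image analysis, has two neuroradiologists, a radiation oncologist and a spine surgeon read the scans blinded to date: "Each of them will compare and choose a better-quality image. These results will be compared and inter-observer variability will be established". The surgeon and radiation oncologist also give a score of 0 to 2 "in terms of confidence in contouring/tumor targeting using a particular image set", for which no analysis is stated.
- **Purpose of the pilot.** Section 2.0, Sample: "Based on results of this study we will perform power analysis". Section 8.0: "Obtained data will be used for designing a larger study". Enrolment is 8 patients, a number the protocol describes as arbitrary.

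**The concern.** The aim compares scans, but the statistic compares readers. High kappa means the readers tended to pick the same scan; it does not say which one. The result named for the primary aim would therefore be the same whether late MRI was nearly always preferred or nearly always rejected.

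The pilot is meant to inform the power calculation of a larger study, and Section 8.0 gives the unknown size of the differences as the reason for having no calculation now. No such size is planned for the primary outcome.

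Section 5.0 has a related gap. The recorded choice is about image quality, whereas the aim concerns the image used to guide management. No item records what the reader would decide from each image set, so the decisions half of the aim could not be tabulated without reading the scans again.

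**Working it through.** The plan has no derived figure to reproduce: n = 8 is arbitrary, and no alpha, power, margin or effect size is given. The check is of what kappa can and cannot show, assuming one forced choice per reader per patient.

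**1. Swapping the labels.** For two readers, let a = both choose late, b = only reader 1 does, c = only reader 2 does, d = neither does, with n = 8. Cohen's kappa is (po − pe)/(1 − pe), where po = (a + d)/n and pe = [(a + b)(a + c) + (c + d)(b + d)]/n². Swapping early and late exchanges a with d and b with c. The sum in po and the two products in pe only change order, so kappa is unchanged.

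Complete enumeration at n = 8 confirms this:
- two readers, Cohen kappa: identical after the swap in 165 of 165 tables;
- four readers, Fleiss kappa: identical in 495 of 495 distributions of late picks.

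Each is undefined only in the two cases where every pick is the same (pe = 1, giving 0/0).

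**2. Worked tables (a, b, c, d).**

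| Table | po | pe | Kappa | Late picks out of 16 reads |
|---|---|---|---|---|
| (6,0,0,2) | 1 | (36 + 4)/64 = 0.625 | 1.00 | 12 (75%) |
| (4,0,0,4) | 1 | (16 + 16)/64 = 0.5 | 1.00 | 8 (50%) |
| (2,0,0,6) | 1 | (4 + 36)/64 = 0.625 | 1.00 | 4 (25%) |
| (6,1,1,0) | 0.75 | (49 + 1)/64 = 0.781 | −0.14 | 14 (87.5%) |
| (0,1,1,6) | 0.75 | (1 + 49)/64 = 0.781 | −0.14 | 2 (12.5%) |
| (7,1,0,0) | 0.875 | (56 + 0)/64 = 0.875 | 0.00 | 15 (93.75%) |
| (8,0,0,0) | 1 | 64/64 = 1 | undefined | 16 (100%) |

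Unanimous readers give 1.0 at every late share from 1/8 to 7/8. If every reader prefers late MRI in all 8 patients, which is the outcome most favourable to the hypothesis, the planned statistic does not exist.

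**3. What the aim asks for.** One reader's proportion choosing late, with exact (Clopper-Pearson) 95% limits at n = 8:

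| Late chosen | Proportion | 95% CI |
|---|---|---|
| 1/8 | 12.5% | 0.3% to 53% |
| 4/8 | 50% | 16% to 84% |
| 7/8 | 87.5% | 47% to 99.7% |
| 8/8 | 100% | 63% to 100% |

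**4. Why the proportion matters for the larger study.** The documents give no margin, so this step assumes one: show that late is chosen in more than p0 of patients, with p0 set 10, 15 or 20 points below 50%. The test is exact binomial, one-sided 2.5%, with 80% power. The table gives the smallest n at which power reaches 80% and stays there for at least 20 consecutive values of n.

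| Assumed p0 | True share 50% | True share 75% | True share 87.5% |
|---|---|---|---|
| 40% (10 points) | 210 | 18 | 10 |
| 35% (15 points) | 94 | 14 | 9 |
| 30% (20 points) | 54 | 11 | 8 |

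A pilot kappa of 1.0 is compatible with every cell.

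**The case against.** The strongest reply is that nothing is lost on the choice outcome. Every paired choice is collected, the protocol says the obtained data (not kappa alone) will inform the larger study, and anyone could count the late choices afterwards. Section 5.0 also says the results will be compared, which could be read loosely to include early against late. This is a non-therapeutic pilot of 8 patients that promises no confirmatory test. Nor does the proposed summary settle the later sample size: the interval at 7/8 contains 50%, 75% and 87.5%, so much of the range in step 4 stays open.

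Parts of this stand. The choices can be tabulated later, so for this half of the aim the fault is in the analysis plan and not in the data. The sizes in step 4 show how much depends on the proportion; they do not measure what the fix gains, and their margins are assumed. A pooled proportion that respects clustering by patient would serve as well as per-reader figures.

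The central point is untouched. The comparison in Section 5.0 is of the readers' choices, its only stated output is inter-observer variability, and no early-late summary is named. Pilot status explains the missing power calculation, but not a missing estimate that the next power calculation needs. For the decisions half of the aim, later tabulation is not available: the confidence score bears on targeting for radiosurgery, but it is not a decision.

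**Conclusion.** The concern holds, and the plan should be changed before the data are analysed. As written, the one analysis assigned to the primary aim cannot say whether late MRI is chosen as often as early MRI. Kappa is the same at mirror-image results, is 1.0 for unanimous readers anywhere from 1/8 to 7/8, and is undefined under complete preference for one scan. These statements need only one forced choice per reader per patient, and they hold for both Cohen and Fleiss kappa. The later-study sizes (for example 94, 14 or 9 patients at a 15-point margin) depend on assumed margins and are illustrative. Separately, the decisions half of the primary aim has no recorded item behind it.

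**What to change.** 1. **Section 8.0, primary summary.** Report, for each reader, the proportion of patients in whom late MRI is chosen, with an exact 95% CI and the patient as the unit. Keep inter-rater kappa as a secondary reliability measure, name its type, and show raw agreement beside it.
2. **Section 5.0, choice question.** Ask which image the reader would use to guide management, or label the result as image-quality preference.
3. **Clinical decisions.** Add one blinded decision item per image set and report within-reader agreement between early and late sets with an exact CI. Otherwise, state that this part of the aim is not assessed.
4. **Confidence score.** Report the paired late-minus-early difference on the 0 to 2 scale as supporting description, not as a primary result.
5. **Interpretation.** State that 8 patients provide estimates and cannot establish that late imaging is equivalent to, or no worse than, early imaging.

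**Cost.** A few sentences in Section 8.0 and a wording change in Section 5.0. The decision item adds 8 patients × 2 image sets × 2 readers = 32 entries if only the surgeon and radiation oncologist answer, or 8 × 2 × 4 = 64 if all four readers do. No new patients, scans or readers are needed. The price is that reading time and a more modest conclusion, because the intervals will be wide.

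### Kappa, the only statistic named for the primary aim, can be zero, negative or undefined at 75–100% raw agreement with 8 patients, and no companion figure is planned

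*Combined protocol and SAP*

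**What the plan says.** The primary aim (Section 2.0) has two parts: whether later MRI leads to the same clinical decisions as early MRI, and whether it "has the same probability of being chosen by a physician for guiding the subsequent management of the patient".

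Section 5.0, Image analysis, has the "images independently reviewed by two neuroradiologists, a radiation oncologist, and a spine surgeon", blinded to acquisition date. "Each of them will compare and choose a better-quality image". Then: "These results will be compared and inter-observer variability will be established".

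On sample size, Section 2.0 says: "We anticipate the initial enrollment of 8 patients, which is a number chosen arbitrary for the pilot study".

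Section 8.0 gives the whole analysis in two sentences: "Kappa statistics will be calculated to evaluate the inter-rater reliability for the primary aim" and "For the secondary aims, descriptive statistics will be used". It adds that the data will serve the design of a larger study.

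The documents do not state the type of kappa (pairwise or multi-reader), a confidence interval, a percent agreement, or what to report if kappa cannot be computed.

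**The concern.** Kappa compares observed agreement with the agreement expected from the readers' marginal choices. When nearly all choices fall on one scan, expected agreement approaches 100% and kappa has little or no room to register real agreement. With only 8 patients, a reader may well pick the same scan every time. Kappa with that reader is then either exactly 0 or, if the second reader does the same, 0/0.

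A strong shared preference for either scan could therefore be reported as unreliable reading, or yield no estimate. A strong preference for the late scan would fit the Section 1.0 hypothesis that later imaging is not inferior. A strong preference for the early scan would be just as important to learn. Because descriptive statistics are tied to the secondary aims, no planned figure would show the reader that agreement was in fact high. That misleading or empty result could then be carried into the design of the larger study.

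**Working it through.** **Inputs.** 8 patients (Section 2.0, Sample) and 4 readers (Section 5.0). Assumptions: the choice is binary, all 8 patients are evaluable, and both readers in a pair have the same preference share *p*. The documents give neither *p* nor an expected kappa, so ranges are used. They state no kappa or precision figure that could be reproduced.

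**Step 1: what kappa gives in possible results.** Kappa = (Po − Pe)/(1 − Pe), where Po is observed agreement and Pe is the agreement expected from the marginals. Cells are: both late / only reader 1 late / only reader 2 late / both early.

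| Cells | Po | Pe | Kappa |
|---|---|---|---|
| 8,0,0,0 | 100% | 1 | 0/0, undefined |
| 7,1,0,0 | 87.5% | 0.875 | 0 |
| 6,2,0,0 | 75% | 0.75 | 0 |
| 6,1,1,0 | 75% | 0.781 | −0.14 |
| 6,1,0,1 | 87.5% | 0.6875 | 0.60 |
| 7,0,0,1 | 100% | 0.781 | 1.00 |

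For 6,1,1,0: Pe = (7/8)² + (1/8)² = 0.781, and (0.75 − 0.781)/(1 − 0.781) = −0.14. The last two rows show that kappa behaves well when the readers share a dissenting patient.

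**Step 2: four-reader (Fleiss) kappa.** Suppose 31 of 32 picks favour one scan. Seven patients have pairwise agreement 1, and one (split 3:1) has 0.5. Mean agreement is 7.5/8 = 93.8%. Pe = (31/32)² + (1/32)² = 0.9395. Kappa = (0.9375 − 0.9395)/(1 − 0.9395) = −0.03. At 32 of 32 it is undefined.

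**Step 3: how often a constant reader forces pairwise kappa to 0 or undefined.** Let q = 1 − p and κ be the true kappa. The cell probabilities are A = p² + κpq (both late), D = q² + κpq (both early) and B = pq(1 − κ) (each discordant cell). The probability that at least one reader of the pair picks one scan throughout is

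2(p⁸ + q⁸) − (A⁸ + D⁸ + 2B⁸).

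At p = 0.9 and κ = 0.6: A = 0.81 + 0.054 = 0.864 and A⁸ = 0.311. The terms in D and B are negligible. The result is 2 × 0.4305 − 0.311 = 0.550. At κ = 0.3: A = 0.837, A⁸ = 0.241, result 0.620.

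| Preference p | κ = 0.3 | κ = 0.6 |
|---|---|---|
| 50% | 1.5% | 1.4% |
| 70% | 10.7% | 9.5% |
| 80% | 28.5% | 24.9% |
| 90% | 62.0% | 55.0% |

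Expected raw agreement at 90% is 1 − 2B = 1 − 2 × 0.09 × 0.7 = 87.4% for κ = 0.3, and 1 − 2 × 0.09 × 0.4 = 92.8% for κ = 0.6. These figures count only failures caused by a constant reader. They exclude negative values and zeros that arise from other tables.

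**The case against.** Several stronger readings are tempting, and the documents do not support them.

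- *A reader might infer that kappa always breaks down under a shared preference.* It does not: 7,0,0,1 gives 1.00 and 6,1,0,1 gives 0.60. An undefined kappa also gives no estimate, which is not the same as reporting no agreement.
- *A reader might cite independent picking at 90% preference.* There, 1 − (1 − 0.4305)² = 68% of pairs are 0 or undefined, with expected raw agreement of 0.9² + 0.1² = 82%. But independent readers have a true kappa of 0, so a kappa near 0 is the right answer. That case is not evidence of failure.
- *A reader might infer that kappa fails in the very result the study seeks.* A strong preference for the late scan fits the Section 1.0 hypothesis. The primary aim in Section 2.0 speaks of equal probability of being chosen. At 50% preference, constant-reader failures affect only about 1.5% of pairs.

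Other objections stand in part. The pairwise rates do not carry over to Fleiss kappa, which is undefined only if all 32 picks match. Under a beta-binomial model at 90% preference, all four readers pick late for a patient with probability 0.757 (intraclass correlation 0.3) to 0.827 (0.6). Over 8 patients that gives 0.757⁸ = 11% to 0.827⁸ = 22%. Near-zero values such as −0.03 remain possible.

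Replacing kappa with a prevalence-adjusted index is also disputable. For independent readers at 90%, Gwet's AC1 is near (0.82 − 0.18)/(1 − 0.18) = 0.78 and prevalence-adjusted kappa near 2 × 0.82 − 1 = 0.64, although there is no agreement beyond chance. An interval from resampling patients would have zero width if all readers agreed throughout.

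Finally, this is a small pilot: "Power analysis was not performed for this pilot study, since magnitude of differences is unknown". No rule says how kappa would enter the later design. That limits the consequence, but it does not supply the missing companion figure.

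**Conclusion.** The concern holds in a limited form. As written, the plan can yield a zero, negative or undefined primary statistic at 75–100% raw agreement, and nothing else is planned for the primary aim that would reveal it. The risk depends on an unknown: it is negligible near balanced preference and affects more than half of reader pairs at 90% preference.

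The rates rest on a binary choice, 8 evaluable patients, equal preference shares within a pair, pairwise kappa and a true kappa of 0.3–0.6. The Fleiss example shows that the problem is not confined to pairwise kappa. None of this addresses the clinical-decision part of the primary aim, for which the documents give no response categories.

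**What to change.** In Section 8.0:

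1. Name the kappa (pairwise, Fleiss or both). Beside it, report raw agreement for each of the six reader pairs, the proportion of patients on whom all four readers agree, and each reader's count choosing each scan.
2. Give exact binomial 95% intervals over patients. These remain usable at the extreme: 8 of 8 gives 63.1% to 100% (lower limit 0.025^(1/8) = 0.631), and 7 of 8 gives 47.3% to 99.7%.
3. State in advance that kappa is shown as *not estimable* when both readers of a pair (or all readers, for Fleiss) pick the same scan for every patient. State also that pairwise kappa is flagged as uninformative when only one reader of the pair does so.
4. Optionally add a prevalence-adjusted index as a sensitivity figure that does not replace kappa.

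This costs a few lines of text and analysis. It uses picks the plan already collects and adds no patients, scans or reads.

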## **9.0 RECORDS/DATA TO BE KEPT**

The data will be stored in a password protected computer in the spine fellow's room, which is a locked room. Paper documents will also be stored in a locked closet in the same room. Alternative location to store data and documents is the PI's office (locked closet and password protected computer). The neuroradiologists may also store data in password protected computers in their reading room.

